#### **14.5.4 Hearing Handicap Inventory**

The Hearing Handicap Inventory (HH) is completed by the Study Participant after indicating his/her agreement to allow randomization in the TRTT, but before the randomized treatment assignment is requested. This form is also completed at the 6-month and 18-month follow-up visits in the TRTT. The HH is a measure of the impact of hearing difficulties on the quality of life. The Clinical Coordinator or Study Audiologist should enter the ID codes for the Study Participant, enter the study visit dates, and review the completed form to make sure all items have been completed. The HH is further described in Chapter 9.

#### **14.5.5 State-Trait Anxiety Inventory**

The State-Trait Anxiety Inventory (SA) is completed by the Study Participant after indicating his/her agreement to allow randomization in the TRTT, but before the randomized treatment assignment is requested. The SA is a measure of anxiety and anxiety proneness. The SA is further described in Chapter 9. The SA is also completed by the Study Participant at the 6 and 18 months follow-up visits. Only the state component of the full State-Trait Anxiety Inventory is collected (the first 20 questions) at follow-up. The Clinical Coordinator or Study Audiologist should enter the ID codes for the Study Participant, enter the study visit dates, and review the completed form to make sure all items have been completed.

#### **14.5.6 Positive and Negative Affect Schedule**

The Positive and Negative Affect Schedule (PA) is completed by the Study Participant after indicating his/her agreement to allow randomization in the TRTT, but before the randomized treatment assignment is requested. The PA is a scale that consists of a number of words that describe different feelings and emotions. This form is also completed at the 6-month and 18-month follow-up visits in the TRTT. The Clinical Coordinator or Study Audiologist should enter the ID codes for the Study Participant, enter the study visit dates, and review the completed form to make sure all items have been completed. The PA is further described in Chapter 9.

#### **14.5.7 Life Events Checklist**

The Life Events Checklist (LE) is completed by the Study Participant after indicating his/her agreement to allow randomization in the TRTT, but before the randomized treatment assignment

is requested. This form is also completed at the 6-month and 18-month follow-up visits in the TRTT. The LE records the occurrence of important life events in the preceding year or the preceding 6 months, and both versions are included in the form. For the Baseline Visit and the 18 month visit, the version requesting information about the preceding year should be administered to the Study Participant. For the 6 month visit, the version requesting information about the preceding 6 months should be administered. The Clinical Coordinator or Study Audiologist should enter the ID codes for the Study Participant, enter the study visit dates, and review the completed form to make sure all items have been completed.

#### **14.5.8 EuroQOL**

The EuroQOL (EQ) is completed by the Study Participant after indicating his/her agreement to allow randomization in the TRTT, but before the randomized treatment assignment is requested. The EQ measures health related quality of life. This form is also completed at the 6-month and 18-month follow-up visits in the TRTT. The Clinical Coordinator or Study Audiologist should enter the ID codes for the Study Participant, enter the study visit dates, and review the completed form to make sure all items have been completed.

### **14.6 Instructions for Forms used to Monitor Adherence to Treatment Protocol**

#### **14.6.1 Treatment Start-up Form**

The Treatment Start-up Form (TS) is completed by the treating Study Audiologist or Clinical Coordinator at time of the first treatment visit. This form is a record of when treatment began. Because the target date for all follow-up visits is linked to the date that treatment was begun, this form is used as the reference to mark the beginning of the follow-up period.

#### **14.6.2 TRT Checklist**

The TRT Checklist (TC) is completed by the treating Study Audiologist during the first treatment visit (T1) for Study Participants assigned to Directive Counseling (DC). The treating Study Audiologist checks whether each task and topic area required by the DC protocol was covered or completed during the DC Session.

#### **14.6.3 Standard of Care Checklist**

The Standard of Care Checklist (SC) is completed by the treating Study Audiologist during T1 for Study Participants assigned to Standard of Care (SC). The treating Study Audiologist checks whether each task and topic area required by the SC protocol was covered or completed during the SC Session.

#### **14.6.4 Sound Generator Issue Form**

The Sound Generator Issue Form (SI) is completed by the Study Audiologist when the sound generator assigned to the Study Participant at randomization is issued to the Study Participant. This form is completed at T1 when a pair of assigned sound generators is obtained from the assigned kit at the Clinical Center and given to the Study Participant. A different form , the Sound Generator Replacement Form (SR)is used to record instances when a replacement sound generator is required, including cases of malfunction, loss, or damage.

#### **14.6.5 Loudness Discomfort Level Assessment for Treatment Form**

The Loudness Discomfort Level (LDL) Assessment for Treatment Form (LD) is completed by the Study Audiologist who is not involved in the treatment of the Study Participant (i.e., who is blinded to the TRTT assignment). It is used to measure the LDL in order to provide information for treatment. It is completed at the second treatment visit (T2) and at the 3-month Follow-up Visits (F1). The Follow-up ATH form includes LDL measurements and is completed during subsequent Follow-up Visits.

#### **14.6.6 Sound Generator Use Form**

The Sound Generator Use Form is completed by the Study Audiologist at T2, and at each follow-up visit. This form is used to record compliance of the individual with the recommended use of the sound generator; record change in volume setting, if required; and discontinuation of sound generator use at the end of treatment.

#### **14.6.7 Follow-up Standard of Care Form**

The Follow-up Standard of Care Form is completed by the Study Audiologist at T2. This form is used to record compliance of the individual with the recommendations given during the standard of care counseling.

## **14.7 Instructions for Forms Completed at Follow-up**

### **14.7.1 Follow-up Medical History Form**

The Follow-up Medical History Form (FM) is completed by the Study Audiologist at the 3, 6, 12, and 18 months Follow-up Visits. Data on the Study Participant's medical condition, medication use, and current noise exposure are recorded on this form.

### **14.7.2 Follow-up Tinnitus Retraining Therapy Interview Form**

The Follow-up Tinnitus Retraining Therapy Interview Form (FT) is completed by the Study Audiologist at the 6, 12, and 18 months Follow-up Visits. This form is used to document perceived changes in the individual's tinnitus, sound tolerance, and hearing status and the impact of each of these components on the Study Participant's health-related quality of life.

### **14.7.3 Follow-up Audiological/Tinnitus/Hyperacusis Form**

The Follow-up Audiological/Tinnitus/Hyperacusis Form is completed by the Study Audiologist at the 6, 12, and 18 months Follow-up Visits. Data on the Study Participant's audiological testing, tinnitus characteristics, and sound tolerance are recorded on this form.

### **14.7.4 Other Follow-up Forms**

All additional follow-up forms are identical to those collected at the Baseline Eligibility Visit (see Sections 14.3 and 14.5). The following forms are collected at all Follow-up visits:

- Tinnitus Questionnaire (TQ)
- Tinnitus Functional Index (TF)
- Tinnitus Handicap Inventory (TI)
- Beck Depression Inventory Fast Screen (BD)

The following forms are collected only at the 6 and 18 months follow-up visits.

- Digit Symbol Substitution Task (DS)
- Hearing Handicap Inventory (HH)
- State Trait Anxiety Inventory (SA)
- Positive and Negative Affect Schedule (PA)
- EuroQoL (EQ)

## **14.8 Instructions for Forms used to Document Study Events**

### **14.8.1 Adverse Event Form**

The Adverse Event Form is completed by the Clinical Center Director (or Study Audiologist, in his or her absence) when an adverse event is identified during the study. If the event has been determined to be a Serious Adverse Event, then this form must be immediately entered into the TRTT online database and the Study Chair notified. If the Adverse Event is not a Serious Adverse Event, then this form must be entered into the online database within one week of becoming aware of the event. Instructions on reporting Adverse Events are included in Chapter 15.

### **14.8.2 Unscheduled Contact Form**

The Unscheduled Visit Form (UC) is completed anytime study-relevant information is obtained outside of a scheduled study visit. Relevant information may include additional information related to counseling or about a Study Participant's status. The Study Audiologist completes this form by recording the topics of conversation covered during the contact. This form is not used to record information related to an adverse event; if an adverse event takes place, an Adverse Event form should be completed.

### **14.8.3 Sound Generator Replacement Form**

The Sound Generator Replacement Form is completed by the Study Audiologist whenever a replacement sound generator is provided to the Study Participant for reasons of malfunction, loss, or damage. It is completed by the Study Audiologist and records the acoustic output of the replacement sound generator

### **14.8.4 Missed Visit/Forms Form**

The Missed Visit/Forms form is used to document a missed Study Visit that will not be able to be re-scheduled and the reason for the missed visit. This form is also used to document if a specific form or forms within a completed Study Visit were not able to be completed and the reasons the forms were not completed.

### **14.8.5 Study Termination Form**

The Study Termination Form is used to document that the status of a Study Participant has changed from active to permanent inactive status (e.g., withdrawn consent to participate) and the

reason for permanent inactive status. This form also documents the death of a study participation and if known, the reason for death.

#### **14.8.6 Participant Transfer Form**

The Participant Transfer Form is used to document when responsibility for a Study Participant is transferred from one Clinical Center to another, along with the reason for the transfer.

#### **14.8.7 Protocol Deviation Form**

The Protocol Deviation Form is used to document any departure from study protocol, the persons responsible, and steps developed to prevent such a departure in the future.

### **14.9 Instructions for Worksheets and Logs**

Worksheets are used to record information that is used within the study, but is not entered online. Logs are forms used to document events that are not entered into the online database.

#### **14.9.1 Audiogram Worksheet**

The Audiogram Worksheet is used as a graphical representation of the audiometric pure tone thresholds, loudness discomfort levels, and tinnitus pitch and loudness match tones and threshold. This worksheet is used for both Directive Counseling and Standard of Care counseling to describe an individual's hearing, tinnitus, and hyperacusis values obtained during an ATH examination.

#### **14.9.2 Baseline and Randomization Checklist**

The Baseline and Randomization Checklist is a worksheet that is comprised of a list of all procedures and forms to be completed at the Baseline Visit and a list of all eligibility criteria. The Clinical Coordinator may use this form to confirm eligibility and completion of all baseline and randomization procedures during and after the Baseline Visit. Because it is a worksheet, it is not entered into the data system.

#### **14.9.3 Kit Log**

The Kit Log is used to document receipt of kits containing the randomized treatment assignment to standard of care or a pair of sound generators (SGs) that have been shipped to the Clinical Center from the DCC. This log is also used to document which kits have been assigned to which Study Participants and the date of assignment. The Kit Log is also used to document the return of malfunctioning and re-issue of devices. This log will be reviewed during Clinical Center site visits (see Chapter 16, Section 16.3).

#### **14.9.4 Shipping Log**

The Shipping Log accompanies any shipment of materials that is sent to another party. It is expected that the shipping log may be used to document shipping CDs or other media with voice recordings of counseling sessions or datalogging files downloaded during sound generator measurement to the DCC. The shipping log may also be used to document shipping a damaged or malfunctioning SGs to GHI

---

### **15.1 Introduction and Definitions**

An adverse event is defined as any unfavorable deviation from baseline health occurring at any time following randomization to the Tinnitus Retraining Therapy Trial (TRTT). Adverse events may be physical, emotional, psychological, or social and may include any illness, sign, symptom, or clinically significant laboratory test or abnormality that has appeared or worsened during the course of the TRTT. The event may or may not be causally related to the treatment intervention.

An *unexpected* Adverse Event is any adverse reaction that has not been previously observed, whether or not the event is anticipated because of the biological properties of the study agent. An *expected* Adverse Event is any adverse reaction whose nature and severity have been previously observed and documented for the study product. There are no known risks for either tinnitus retraining therapy or the standard of care for severe tinnitus, and so there are no expected Adverse Events.

A Serious Adverse Event (SAE) is further defined as meeting one of the following conditions:

- Death;
- Life threatening;
- In-patient hospital admission, or prolongation of an existing hospitalization;
- Results in congenital anomaly or birth defect;
- Results in a persistent or significant disability or incapacity; or
- Results in need for medical intervention.

Important medical events that may not result in death, be life threatening, or require hospitalization, may be considered an SAE when based on appropriate medical judgment, as they may jeopardize the Study Participant and may require surgical, medical, or psychological intervention to prevent one of the outcomes listed in this definition.

Events not considered to be an SAE are hospitalization occurring under the following circumstances:

- Planned before entry into the TRTT;
- For elective treatment of a condition unrelated to the Study Participant's tinnitus;
- Take place as an emergency, outpatient basis and do not result in admission; or
- Are part of the normal treatment or monitoring of an existing condition.

There is a distinction between an SAE and a severe adverse event. An SAE is a regulatory definition as described above. The severity of an adverse event is an intensity classification and may be mild, moderate, severe, or life threatening. The following definitions apply:

**Mild:** Transient or mild discomfort (<48 hours); no medical intervention/therapy required

**Moderate:** Mild to moderate limitation in activity; some assistance may be needed; no or minimal medical intervention/therapy required

**Severe:** Marked limitation in activity, some assistance usually required; medical intervention/therapy required; hospitalization possible

**Life threatening:** Extreme limitation in activity, significant assistance required; significant medical intervention/therapy required, hospitalization or hospice care possible

An Adverse Event is also defined by its relation with the treatment intervention, as follows:

**Definite:** Clear-cut temporal association, and no other possible cause

**Probable:** Clear-cut temporal association, and a potential alternative etiology is not apparent

**Possible:** Less clear temporal association; other etiologies are also possible

**None/Not Related:** The adverse event is completely independent of intervention administration; and/or evidence exists that the event is definitely related to another etiology.

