### **12.2.2 Ear Canal Impressions**

Most Study Participants who meet eligibility criteria for inclusion in the study and who willingly agree to participate will have outer-ear-canal impressions made bilaterally subsequent to completing informed consent. This activity may be performed at the Baseline Visit or during a subsequent Randomization Visit at the discretion of the Study Audiologist.

The Study Audiologist will take impressions of both of the Study Participant’s outer-ear canals following the checklist and protocol outlined in Table 1. The first step in taking the impressions is to explain to the Study Participant how an impression is made and the purpose of taking an impression. This explanation will allay any fears that he or she may have about the procedure. The Study Audiologist will inform the Study Participant that the impression of the outer-ear canal is made with a soft material that must set up for about ten minutes. It also is important to explain that in some cases the first impression of the ear canal with the jaw open will not produce a good fit, and that a second impression will be taken with the jaw closed to

assure a good and comfortable fit with one of the two sets of impressions. The Study Participant will be instructed to continue to wear his or her glasses and dentures, if these are present, during the impression-taking protocol. Occasionally, it may be necessary to make a second impression for one or more of these opened- or closed-jaw conditions. If the definition of the completed impression does not adequately capture the anatomy of the outer ear and ear canal.

The Study Audiologist will then gather the materials and tools needed to take the impression, and place a bite-block between the molars for the open-jaw impressions. Next, an examination of the ear canal will be conducted using an ear light or an otoscope to assess the:

- Size of the impression needed;
- Length, direction, and diameter of the ear canal;
- Shape and contours of the external ear and canal; and
- Presence of any impediment to taking an impression (e.g., wax, enlargement, trauma, etc.).

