When the external ear has been filled completely, the Study Audiologist will use his or her finger (not palm) to touch and gently smooth the impression material in the concha and helix areas. It is critical to fill the helix, but care should be taken not to overfill the impression material, which may distend the outer ear and confound the mold of the outer ear and ear canal. Subsequently, an impression is made immediately for the opposite ear so that both impressions can cure simultaneously. After an adequate period to allow the impression material to set, the ear canal impression should be removed.

To remove an impression, the Study Audiologist will gently press the ear away from the impression; remove the helix curl slightly and bring the impression straight out while holding the ear canal block thread. It is best to pull gently and steadily so as not to distort the impression. After the cured impressions are removed from the ears, and otoscopic examination should be performed to ensure that all impression material has been removed from each ear and confirm that there are no abrasions of the ear canals or ear drum as a consequence of performing the protocol.

The Study Audiologist will then check to make sure that the impression adequately mirrors the outer-ear canal and that each helix and concha are well-formed along with the external ear canal portion. If an impression is flawed, then it will be necessary to take a second impression. If it is adequate, then the impression will be labeled and prepared for shipping to GHI. The protocol then will be repeated for the closed-jaw condition, but with the bite-block removed from the mouth.

Each impression should be labeled either either "opened-jaw" or "closed-jaw" and either "left" or "right" ear. The shipment of the impressions to GHI will therefore include two sets of impressions for each ear as well as a Sound Generator Request Form identifying the Study Participant and including the address to which the devices should be sent. Impressions will be

shipped by Federal Express overnight delivery to ensure preparation and return of the SG from the manufacturer to the Clinical Center in time for the Initial Treatment Visit (T1). At the time the impression is sent from the Clinical Center, both the DCC and GHI will be notified and, similarly, upon return of the SGs to the Clinical Center, the DCC and Clinical Center will be notified of shipment.

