- **Schedule of use** – Wear the instruments as much as possible throughout the day. If you can’t wear them all day, wear them at least 8 hours. That does not have to be all at one time and it does not have to be the same schedule every day. The wearing time can be built up over the next few weeks. Wear the instruments even if the tinnitus is not present. You can wear them to sleep, if they are comfortable, but the sleep time does not count toward the 8 hours. Put the instruments on as soon as you wake up unless you shower in the

morning. Dry your ears and put them on after that. At any time, if the instruments are physically uncomfortable, at any time, contact the Audiologist.

- **Avoid silence** – It is important to keep a low level of **neutral** environmental sound on at all times in addition to the SGs. The background sound does not have to be loud and should not mask the tinnitus. The sound should not be annoying. Use a fan, computer, nature tapes, sound machine, car sound, humidifier, aquarium, or other low level constant sound. A sound machine, sound pillow ([www.soundpillow.com](http://www.soundpillow.com)) fan, or humidifier can help during sleep. Try not to use TV or talk radio at night so that your brain does not “tune in” to something that is interesting. **When you are surrounded by normal environmental sounds, you may not be aware of the sound from the instruments.**
- **Keep the focus off the tinnitus.** Do not keep diaries or journals. Tell family and friends not to ask how you are doing. Do not worry about normal fluctuations in tinnitus from caffeine, wine, alcohol, chocolate, exercise, naps, etc. These can make the tinnitus **worse or better**, but these changes are typically temporary. Do the things you want to do and live your life without worrying about these fluctuations.
- **Six-week effect** – Do not worry if the tinnitus gets “worse” after a few weeks of wearing the instruments. It is very common and very temporary. The brain may be adjusting to this new signal.

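### Section 15.1 says no adverse events are expected although Chapter 12 documents a common worsening after device start, and ear-impression injuries before randomization have no reporting route in Chapter 15

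*Combined protocol and SAP*

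**What the plan says.** - **Definition and start.** Section 15.1 defines an adverse event as "any unfavorable deviation from baseline health occurring at any time following randomization". New or worsened symptoms are included, whether or not treatment caused them. A serious adverse event is an adverse event that meets further conditions.
- **Expectedness.** The same section calls an event expected if it is "any adverse reaction whose nature and severity have been previously observed and documented for the study product", and unexpected if it has not been seen before. It then says that neither treatment carries a known risk, and draws this conclusion: "and so there are no expected Adverse Events".
- **Six-week effect.** The fitting script (Chapter 12, Appendix B) tells device users not to worry if tinnitus gets worse some weeks after they start wearing the instruments: "It is very common and very temporary". The participant handout (Chapter 12, Appendix C) repeats this.
- **Ear impressions.** Section 12.2.2 says of taking impressions: "This activity may be performed at the Baseline Visit or during a subsequent Randomization Visit", at the audiologist's discretion. An otoscopic check afterwards must "confirm that there are no abrasions of the ear canals or ear drum as a consequence of performing the protocol". Table 1 of Chapter 12 adds bleeding and swelling to that check.
- **Reporting rule.** Section 15.2.2 asks staff to report all non-serious events. It requires an Adverse Event Form if any one of three triggers is met: the event was unexpected; it was not a risk named in the consent and the intervention may have caused it; or there is doubt about reporting it to the IRB.

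**The concern.** A safety chapter should agree with what the rest of the manual tells staff and participants to anticipate. Here the audiologist reads aloud that a worsening is common, while Chapter 15 says nothing is expected. Two sites could handle the same episode differently, each with text to support it. Section 19.3.8.1 makes detection of adverse reactions by arm a main purpose of the six-monthly DSMB report, so consistent classification matters.

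The start date is a separate problem. A study procedure with foreseen local injury may take place before the adverse-event definition begins to apply. What is at stake there is oversight of participants, not the estimate of treatment effect.

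**Working it through.** No formula applies and the plan gives no figure to reproduce. The check sets the passages side by side.

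**1. Is the six-week effect an adverse event?** Yes. It is a symptom that worsens after randomization, and 15.1 requires no causal link.

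**2. Is it expected or unexpected?** The script and handout record it as already observed with device use, so it fails the definition of unexpected in 15.1. It fits the definition of expected, with one reservation: that definition also asks for documented severity, and Chapter 12 gives only frequency and duration. The closing statement of 15.1 nevertheless says that no expected events exist. Taken together, the effect has no consistent class.

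**3. What follows under 15.2.2?**
- A site that follows the closing statement of 15.1 treats every event as unexpected. The first trigger applies and a form is filed each time.
- A site that follows the definitions, or the script, does not regard the worsening as unexpected. The first trigger drops out. A form then depends on the consent's risk list, on doubt about IRB reporting, or on the general instruction that opens 15.2.2.

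**4. Would scheduled visits catch it?** Section 22.2.5 (printed as 221.2.5) places visits at 1, 3, 6, 12 and 18 months after the first treatment visit. Taking the label literally, 6 × 7 = 42 days. One month is about 365 / 12 = 30 days and three months about 91 days. The episode would start about 42 − 30 = 12 days after the one-month visit and 91 − 42 = 49 days before the next. The one-month forms in 14.6.5 to 14.6.7 cover loudness discomfort, device use and standard-of-care compliance. The Tinnitus Questionnaire and the Follow-up Medical History start at 3 months (14.7.1, 14.7.4). A worsening that has resolved by then need not show in those scores.

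**5. Are impression injuries covered?** By 15.1, events count when "occurring at any time following randomization". An abrasion from an impression at the Baseline Visit comes earlier, so it is not an adverse event. Because serious events are a subset, even a serious injury at that point lies outside Chapter 15. Otoscopy should detect it, but the chapter gives no form or route to record it. Since it precedes assignment, it cannot differ systematically by arm.

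**The case against.** The strongest reply is 15.2.2. If nothing is expected, every event after randomization is unexpected, triggers a form and goes to the DSMB. On that reading the criticized sentence widens capture. This largely stands. A reader might infer that device-related harms will be missed, and the documents do not support that. What remains is that the broad reading asks staff to file as unexpected an effect they have just called common, against the section's own definition.

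A reader might also infer that the DSMB's comparison of harms is unsound because only device users are told not to worry. That goes too far. Only they receive the six-week message, but standard-of-care participants are told that tinnitus may worsen (Chapter 13, Appendices A and C), that benefit fluctuates (13.4), and that setbacks occur and slow progress is normal (Chapter 13, Appendix B). Both device groups receive the same script, so it gives no reason for different reporting between conventional and placebo devices. A difference between device users and standard of care is possible, but it is inference. Tinnitus scores and the depression screen are collected in all arms from 3 months.

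The expectedness label also has limited reach: under 15.2.1 it affects prompt reporting only when an event needs medical or psychological intervention.

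The impression gap is narrow. It covers only the interval from an impression to randomization. Impressions serve the in-the-ear devices preferred part-way through the trial (21.3.3), and 12.2.1 places the device order after randomization. Section 12.2.2 still permits the earlier timing, and 15.2.2 does nothing for events before randomization.

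Finally, Part 1 of the manual and the consent text were not available. They may list risks or give another reporting route.

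**Conclusion.** The point holds as two separate defects, both modest.

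- **Classification.** The statement that no adverse events are expected conflicts with 15.1's own definitions once the six-week effect is taken into account. The worsening may be classified or reported inconsistently, and a brief episode may resolve between the one- and three-month visits. This is a risk that depends on how sites read the text, not a certain loss of data.
- **Start of collection.** An impression injury before randomization has no reporting route in Chapter 15. This is a participant-protection gap and does not bias the arm comparison.

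The size cannot be given as a count. Section 21.3.1 expects about 76 participants per device type, so about 2 × 76 = 152 would receive the six-week message. It is tempting to multiply that by an assumed rate, but the documents say only that the effect is very common. Any such count would also assume that every episode is missed or misfiled, which 15.2.2 does not support.

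The conclusion rests on the chapters available, on reading the six-week label as the approximate time of onset, and on visits taking place near their target dates.

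**What to change.** 1. In 15.1, replace the statement that no events are expected. List as expected the transient tinnitus worsening after device start, and ear-canal irritation or abrasion from impressions or devices. This reconciles 15.1 with Chapter 12, Appendices B and C, and with 12.2.2.
2. In 15.2.2, state that an Adverse Event Form is still required for these listed events. Without this, listing them would remove the first trigger, and naming them in the consent would remove the second, so reporting could fall.
3. Start adverse-event collection at the first study procedure after consent, so that impressions at the Baseline Visit are covered.
4. Ask one identical question about worsening, with recall since the last visit, at the one-month and three-month visits in all three arms. The one-month visit alone would come too early for an effect at about six weeks.

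The counseling text need not change. The cost is edits to 15.1, 15.2.2 and the Adverse Event Form, one added question at two existing visits, and slightly more recorded events. Before the edits are made, Part 1 and the consent text should be checked for any risk list or reporting route that already covers these events.
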